## JHM IRB - eForm A – Protocol

- Use the section headings to write the JHM IRB eForm A, inserting the appropriate material in each. If a section is not applicable, leave heading in and insert N/A.
- When submitting JHM IRB eForm A (new or revised), enter the date submitted to the field at the top of JHM IRB eForm A.

\*\*\*\*\*

### 1. Abstract

- a. Provide no more than a one page research abstract briefly stating the problem, the research hypothesis, and the importance of the research.

Gastrointestinal (GI) dysmotility is common in GI motility disorders, such as functional dyspepsia (FD) gastroparesis and chronic constipation. The symptoms of GI dysmotility include abdominal discomfort or pain, early satiety, nausea, vomiting, abdominal distension, bloating, anorexia and reduced bowel movement. Medical treatment for GI motility disorders is very limited in the US. Acupuncture has frequently been used for treatment of GI ailments in Eastern countries. The most commonly used acupuncture points (acupoints) for focused treatment of GI symptoms are the Neiguan (PC6) and the Zusanli (ST36) points. Electroacupuncture (EA) at PC6 and ST36 has been reported to accelerate gastrointestinal motility in both animals and human.

Recently, we have studied the feasibility of transcutaneous electroacupuncture (TEA): electrical stimulation is applied to acupoints via surface electrodes without needles, similar to the commercial available transcutaneous electrical nerve stimulation (TENS) but applied to acupoints. We hypothesize that TEA as a new treatment option, improves GI symptoms in patients with FD, gastroparesis or constipation, improves GI motility and therefore improves quality of life of the patients.

The success of this project will lead to a noninvasive and convenient therapy for treating GI motility disorders. The proposed TEA method is expected to improve gastric and colonic functions and thus improve quality of life. In addition, the proposed TEA method and device are self-administrative after training during the first office visit. It provides a long-term treatment option for both FD, gastroparesis and chronic constipation.

### 2. Objectives (include all primary and secondary objectives)

1. Effects of TEA on GI symptoms, in patients with FD or gastroparesis or chronic constipation.
2. Mechanisms of TEA for treating GI motility disorders: TEA improves gastric accommodation, gastric dysrhythmia, and the improvement in these pathological abnormalities may be associated with the enhancement of vagal activity and the release of GI hormones.

3. **Background** (briefly describe pre-clinical and clinical data, current experience with procedures, drug or device, and any other relevant information to justify the research)

FD affects millions of Americans but is difficult to treat due to its multiple abnormalities in gastric motor and sensory functions. Common treatment options include dietary measures, pharmacologic treatments, such as acid-suppression drugs, prokinetic agents, fundus relaxing drugs, and antinociceptive agents, and psychologic interventions (1-3). In general, targeted therapies directed at the underlying pathophysiology are desirable. However, efficacy of the therapy is usually very limited due to multiple symptoms and pathophysiologies in individual patients. For example, a patient may have impaired accommodation and delayed gastric emptying at the same time; in this case, prokinetic agents can be used to treat delayed emptying but would worsen the symptoms related to gastric accommodation because available prokinetics often impair gastric accommodation. For the same reason, fundus relaxing drugs may be used for treating impaired accommodation; however, these drugs may delay gastric emptying because they relax muscles. The treatment approach to patients with hypersensitivity to gastric distension has not been established. Antidepressants are commonly used in functional GI disorders and were thought to exert a visceral analgesic rather than an antidepressant effect. However, studies of the effects of antidepressants on visceral sensitivity are rare, and the existing data on visceral sensitivity are controversial (4).

Gastroparesis is defined as delayed emptying of solids from the stomach. The common symptoms of gastroparesis are similar to FD, resulting from impaired gastric motility. Same as FD, currently very limited treatment options are available for gastroparesis. A number of prokinetics were developed for treating gastroparesis but have been withdrawn from the market due to their side effects.

Constipation is highly prevalent in the US. Currently most patients are dependent on laxatives that do not cure the disease and long-term use may actually worsen the condition. In addition, due to an alarming increase in the use of opiates for pain, opiate-induced constipation became a big medical problem.

Acupuncture is a Traditional Chinese Medicine method which has been used in the treatment of patients for thousands of years. Acupuncture is being increasingly accepted by practitioners and patients in the West as well, especially during the last three decades. Electroacupuncture (EA) is a modification of this technique that stimulates acupuncture points (or acupoints) with electrical current instead of manual manipulations, and appears to have more consistently reproducible results in both clinical and research settings. EA has been used to treat GI symptoms, including acute and chronic gastroenteritis, diarrhea, constipation, vomiting, nausea, and gastroduodenal ulcers by altering acid secretion, GI motility, and visceral pain (5-6). The most commonly used EA points in treating GI symptoms are the Zusanli point of the lower limbs (stomach-36 or ST-36) and the Neiguan point at the wrist (pericardium-6 or PC-6). EA at PC6 and ST36 has been shown to improve gastric motility in both animals and humans (7-8). Recently, a number of studies have been performed to examine the efficacy of EA for the treatment of visceral pain. It has been shown that repeated EA attenuated visceral hypersensitivity in irritable bowel syndrome (IBS) rat model (9), and EA at ST-36 and PC-6 significantly increases the threshold of rectal sensations to rectal distension in IBS patients (10-11). It remains to be investigated whether EA improves GI symptoms, motility in patients with FD or gastroparesis.

Recently, we have studied the feasibility of transcutaneous electroacupuncture (TEA): electrical stimulation is applied to acupoints via surface electrodes without needles. This method is similar to the commercial available transcutaneous electrical nerve stimulation (TENS) but applied to acupoints. Compared to the traditional EA, TEA is needless, self-administrative, therefore may benefit patients with impaired gastric motility.

We hypothesize that TEA as a new treatment option, improves GI symptoms in patients with FD gastroparesis or chronic constipation, accelerate impaired GI motility and therefore improves quality of life of the patients.

#### 4. Study Procedures

##### a. Study design, including the sequence and timing of study procedures

A double-blinded crossover design will be used for the study (Fig. 1). Forty patients with FD, forty patients with gastroparesis and forty patients with chronic constipation will be blinded about the treatment regimens and patients who are familiar with the acupoints or meridian will be excluded.

Revisions to the informed consent process are being permanently adopted for this research. Teleconsent will be used as opposed to in person consenting where possible to reduce unnecessary in person encounters specifically for a consent procedure. In the event teleconsent is utilized, participants will be provided with a copy of the Informed Consent prior to the teleconsent meeting either via email, fax, mail or previously provided during an in person visit.

Participants will be given adequate time to consider the research study and ask questions prior to signing the consent form. The consent designee must verify the participant physically signed the consent document either by viewing via video conference, obtaining a photo of the signed consent document; or obtaining verbal confirmation from the participant that he/she signed the consent form or agreed to participate electronically. The participant will sign and date/time the informed consent document. The document is then mailed, emailed or faxed to the consent designee. The participant will be asked to return the original signed document on their first in person visit. If the Informed Consent form is mailed to the consent designee by the participant the study coordinator will sign the copy, which they possess after the participant has acknowledged signature on their copy. Once the original is received by the consent designee the copies will be attached to make a single document. In all other instances, once received, the research coordinator signs, dates/times the informed consent document.

At the time of the first clinical encounter post teleconsent, research coordinator will review any additional study participant questions and discuss the risks, benefits and alternatives of the study in full detail, completing the physician/mid-level component of the consent process. After the Informed Consent process is completed, a study team member will file the consent document in EPIC. The entire consent document is also then filed in the research record.

Upon enrollment, each patient will be randomly assigned to group A or group B. Patients in group A will be treated with TEA at ST36 and PC6 for 4 weeks, followed with a 2-week washout period and another 4-week period with sham TEA. Patients in group B will be treated with TEA and sham-TEA in a reversed order. The previous preliminary studies with EA or TEA were of duration of 2 weeks. To ensure better performance, we choose a treatment period of 4 weeks. A previous study has indicated that a washout period of 2 weeks is sufficient. The patients will not be informed of the exact locations of ST36 or PC6 and will not be informed that TEA at the sham points may be ineffective. The patients will be asked to come to the hospital 4 times: before the study (V1), end of the first 4 weeks (V2), end of washout period or beginning of the second 4-weeks (V3) and end of the second 4 weeks (V4). TEA or sham TEA will be performed three times daily, each initiated immediately after a meal and lasts for 2 hours. Various tests will be performed during each visit (see Fig.1 and Table 1). Symptoms of gastroparesis, assessment of constipation and questionnaire of quality of life (SF-36) as well as

TEA usage questionnaire will be completed during each of the 4 visits. The questionnaires will also be completed by the patient at home at the end of each week including the washout period.

The procedure for each visit is as follows: In the morning, GI symptom questionnaire, TEA use and SF-36 will be completed; then chest and abdominal surface electrodes will be placed and the noninvasive measurements of electrogastrogram (EGG) will be recorded for 2 hours. One hour after the recording, a test meal will be consumed by the subject and the recording will be continued for one more hour. Blood samples will be taken to measure gastrointestinal hormones such as NPY, ghrelin, CCK, motilin and VIP at different time points: at the initiation of the baseline recording of the EGG, immediately before the ingestion of the meal, 30 and 60min after the test meal. TEA or sham-TEA (according to the preceding treatment regime) will be performed during the tests for visits 2 and 4. No TEA or sham-TEA will be performed during visits 1 and 3 as these tests will be considered as baseline or control tests. For the patients with chronic constipation, no nutrient drink test will be conducted, symptoms related to constipation will be assessed, EGG will be recorded and blood samples will be collected.

[figure not shown]

Table 1: Measurements during each of the scheduled visits (For patients with FD or Gastroparesis)

Time	GI Symptom Questionnaire	TEA Use	SF-36	EGG	Blood
Week 0 (V1)	+		+	+	+
Week 1	+	+			
Week 2	+	+			
Week 3	+	+			
Week 4 (V2)	+	+	+	+	+
Week 6 (V3)	+		+	+	+
Week 7	+	+			
Week 8	+	+			
Week 9	+	+			
Week10 (V4)	+	+	+	+	+

Notes:

- Abbreviations: V: visit; EGG: electrogastrogram.
- TEA Use questionnaires will be administered by telephone during weeks 1-3 and 7-9.

### Transcutaneous electroacupuncture

*Location of acupuncture points:* Two acupoints, ST36 (Zusanli) and PC6 (Neiguan) will be chosen for the TEA therapy. These two acupoints have been traditionally used to heal the ailment of stomach and frequently chosen in research studies, including our previous studies (13-15). PC6 is a common acupuncture point used for the treatment of nausea and vomiting,

whereas ST36 is one of the most frequently used acupuncture points for the treatment of gastric diseases. These two points were also used in our previous studies in humans and were shown to be effective in treating dyspeptic symptoms and improving gastric motility (13-15). The location of ST36 (Zusanli) is at the depression inferior to tibia tubercle and one finger-breadth (the patient's thumb finger) from the anterior crest of the tibia. Anatomically, it is between the muscle anterior tibialis and muscle extensor digitorum longus. Superficially, there are the lateral sural cutaneous nerve and the cutaneous branch of the saphenous nerve at this acupoint. Profoundly, there is the deep peroneal nerve (16). PC (Pericardial meridian) 6 (Neiguang) is located at the junction of the distal one sixth and the proximal five sixth from the transverse crease of the wrist to the transverse cubital crease, between the tendons of m. palmaris longus and m. flexor carpi radialis. Superficially, there is muscle flexor digitorum superficialis at the location. Profoundly, there is muscle flexor digitorum profundus. The medial antebrachial cutaneous nerve, the median nerve (deeper) and the anterior interosseous nerve (deepest) are distributed at the location.

*TEA and sham-TEA:* TEA will be performed continuously for 2 hrs immediately after each meal. The patient will be trained by the unblinded stimulator programmer to place electrodes in the right locations of the body and will not be told whether the points are sham or real. Two electrodes will be placed for each acupoint: one right at the acupoint and the other 4 to 6 cm away from the acupoint along the meridian of the acupoint (Fig.2). One PC6 point and one ST36 point will be used. Fig.2 shows the placement of stimulation electrodes and stimulator at the PC6 point. Weak electrical pulses are delivered from the stimulator (the wrist watch-like unit).

Sham-TEA will be performed using sham-points with the same output from the stimulators. The sham points for PC6 and ST36 will be at non-acupoints a few centimeters away from the real points between meridians.

Trains of pulses will be used for TEA or sham-TEA with train on-time of 2sec and off-time of 2sec. Pulses in each train will have a frequency of 25Hz and an amplitude range of 2-10mA, based on patient tolerability. These parameters were previously shown to be effective in treating GI symptoms in patients with scleroderma and FD (13, 14).

When TEA is performed outside hospital, the patient will be asked to continue his or her regular activity. Instructions for the use of the device by the patient at home will be given and include the following: 1) a picture showing the locations where the electrodes should be attached; 2) placement of stimulators; 3) instructions for turning on and off the micro-stimulator (all stimulation parameters will be programmed by the investigator and not alterable by the patient); 4) a timer will be given to the patient and the patient will be reminded when the stimulator should be disconnected to the electrodes; 5) instructions for the removal and storage of the electrodes and stimulator as well as charge of the stimulators.

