#### **Assessment of gastroparesic symptoms, quality of life and use of TEA**

Dyspeptic and gastroparesic symptom questionnaire will use the previously validated gastroparesis cardinal symptom index (17), including 9 symptoms: nausea (feeling sick to your stomach as if you were going to vomit or throw up), retching (heaving as if to vomit, but nothing comes up), vomiting, stomach fullness, not able to finish a normal sized meal, feeling excessively full after meals, loss of appetite, bloating (feeling like you need to loose your clothes) and stomach or belly visibly larger. Each symptom will be graded from 0 to 5 (none, very mild, mild, moderate, severe and very severe).

Quality of life questionnaire Health-related QOL (HR-QOL, or QOL) symptom assessment will be performed using the validated SF-36 health form questionnaire with its specific scoring system.

Fig.2: The micro-stimulator (watch-like) to be used for TEA.

TEA use questionnaire 1) How many meals did you eat in the last 7 days? 2) How many of these meals did you apply the TEA? 3) When you use the TEA, about how long do you wear the stimulators?

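### Electrode site is the only difference between TEA and sham, yet nothing checks or records where patients place the electrodes, so a wrong-site session can deliver the other condition and still count as compliant

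*Combined protocol and SAP*

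**What the plan says.** **The contrast.** Section 4a, Transcutaneous electroacupuncture, makes the electrical side of the two treatments the same: "Sham-TEA will be performed using sham-points with the same output from the stimulators". What differs is position: "The sham points for PC6 and ST36 will be at non-acupoints a few centimeters away from the real points between meridians". No exact offset or landmark is given for the sham points. Each real point takes two electrodes, "one right at the acupoint and the other 4 to 6 cm away from the acupoint along the meridian of the acupoint".

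**Who places the electrodes.** The same section states: "The patient will be trained by the unblinded stimulator programmer to place electrodes in the right locations of the body". The home instructions add "a picture showing the locations where the electrodes should be attached". Stimulation settings are locked against the patient and a timer is supplied.

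**What is recorded.** The TEA-use questionnaire asks how many meals were eaten, "How many of these meals did you apply the TEA", and how long the stimulators were worn. It has no item on location. Under Table 1 it is given by telephone in weeks 1-3 and 7-9. Section 7c builds the weekly compliance covariate from this questionnaire alone.

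**The crossover.** Every patient is assigned one set of sites for four weeks, has two weeks of washout, and is then assigned the other set. TEA or sham is also applied in hospital during the tests at V2 and V4.

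**The concern.** The plan controls what is common to both treatments (settings and session length) and leaves unobserved the one thing that differs. Training and a picture help to prevent error, but neither shows afterwards where the electrodes were.

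The crossover adds a specific route for error. By period 2 a patient has used one set of sites for four weeks and must now use another a few centimetres away. Blinding means that the patient does not know which set is which and has little means of noticing a lapse. If a group A patient goes back to the TEA sites during the sham period, the sham period contains active treatment. If a group B patient goes back to the sham sites during the TEA period, the TEA period contains sham. Both lapses shrink the difference. The compliance covariate cannot adjust for them, because a full-length session at the wrong site scores as a perfect one. A null result could then not be told apart from misplacement.

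**Working it through.** **Inputs.** From section 7c: SD 38, correlation 0.4, 40 patients per disease, 8 weekly observations (4 per period), two-sided 0.05, and 80% power at 10-11 percentage points. From section 4a: three sessions a day for 4 weeks. The misplacement share m is not in the documents; I use 5%, 10% and 20% as assumptions.

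**1. Exposure.** 3 x 28 = 84 prescribed sessions per period. This is an upper bound on home sessions, since it assumes three meals every day and includes stimulation given at V2 and V4.

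**2. What the data would show.** Suppose that a group A patient uses the period-1 sites after all 3 x 7 = 21 meals of week 7, for 2 hours each. The questionnaire returns 21 meals, 21 with TEA, 2 hours: 100% compliance with sham.

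**3. The plan's own power figure.** With patient fixed effects and equal correlation, SE = sqrt(38² x (1 - 0.4) x 2 / (4 x 40)) = sqrt(10.83) = 3.29. The detectable difference is (1.96 + 0.84) x 3.29 = 9.2 points, against the stated 10-11. Power at 10, 10.5 and 11 points is 86%, 89% and 92%; a simulation of the treatment, patient and period model gave 87%, 89% and 92%. The stated figure is therefore not reproduced and is conservative on these inputs. That does not affect the present point, but it gives two starting levels, and I show both.

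**4. Dilution.** Take the effect as proportional to the share of sessions at the active sites, and let d be the true difference.
- *Period-2 reversion.* Group A: TEA gives d and sham gives md, so the contrast is (1 - m)d. Group B: TEA gives (1 - m)d and sham gives 0, so again (1 - m)d.
- *One-way drift of TEA sessions to sham sites.* Also (1 - m)d.
- *Swaps in both periods.* (1 - m)d - md = (1 - 2m)d.

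**5. Power.** Power = Phi(k x f - 1.96), where f is the dilution factor. Calibrated to the stated 80%, k = 2.80. On the plan's inputs at 10.5 points, k = 10.5 / 3.29 = 3.19. Example: m = 10%, f = 0.9, k = 2.80 gives Phi(0.56) = 71%.

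| m | Stated 80%, factor 1 - m | Stated 80%, factor 1 - 2m | Plan inputs (89%), factor 1 - m | Plan inputs (89%), factor 1 - 2m |
|---|---|---|---|---|
| 5% | 76% | 71% | 86% | 82% |
| 10% | 71% | 61% | 82% | 72% |
| 20% | 61% | 39% | 72% | 48% |

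**6. True difference needed to observe 10.5 points.** 10.5 / (1 - m) = 11.1, 11.7 and 13.1 points; 10.5 / (1 - 2m) = 11.7, 13.1 and 17.5 points, for m = 5%, 10% and 20%.

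**The case against.** **Placement is not left to chance.** The training sentence stands in the paragraph on both TEA and sham TEA, so it covers both conditions, and section 4c has the investigator locating real and sham points. This stands: prevention is planned. What is missing is verification and a record.

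**No training at V3.** A reader might infer this from the abstract, which calls the method "self-administrative after training during the first office visit". That sentence describes the convenience of the method and is not a visit schedule. A change of sites all but requires new instruction at V3. The documents simply do not describe it.

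**Every misplaced session becomes the other treatment.** A reader might infer this too, but the text does not support it. An electrode off the acupoint approximates sham, whereas a misplaced sham electrode normally lands on another non-acupoint and stays sham. It becomes active only on or near the real point. Return to the period-1 sites is the case that truly swaps conditions.

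**The sham offset is smaller than the electrode spacing.** This is not shown. A few centimetres is not a figure, and the 4 to 6 cm spacing runs along the meridian while sham points lie between meridians. The distances are of the same order; no more can be said.

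**The largest power losses do not fit the likeliest mechanism.** Correct. Reversion to sites taught earlier can happen only in period 2, so the factor is 1 - m. On the plan's own inputs, 10% reversion still leaves about 82% power with complete follow-up.

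**Correcting patients may unblind them.** This stands as a cost: feedback has to be worded neutrally.

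**Conclusion.** The point holds in a limited form. Electrode site is the whole treatment contrast, home placement is neither checked nor recorded, and the compliance covariate cannot see a wrong-site session. Such sessions bias the comparison towards no difference, and the loss cannot be measured or repaired afterwards.

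The size is conditional. Under the most plausible route, period-2 reversion at 5% to 20%, power falls from the stated 80% to 76%-61%, or from about 89% to 86%-72% on the plan's own inputs. The (1 - 2m) columns are a worst case, requiring swaps in both periods. All of this rests on assumed values of m, on an effect proportional to the share of sessions at the active sites, and on complete follow-up. The documents do not show that misplacement will be common, and they do not support calling the trial underpowered on this ground. The case for change is that the remedy is cheap and supplies information that the trial would otherwise lack.

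**What to change.** 1. At V1 and V3, train only the current period's sites, and have the patient demonstrate correct placement before leaving.
2. At V2 and V4, before the in-hospital session, have the patient place the electrodes without help. The unblinded programmer already in the plan records right or wrong site on the case report form before any correction.
3. At V2, once that check is done, collect the period-1 picture; issue the period-2 picture at V3.
4. Report wrong-site frequency by treatment and period beside the primary result. Do not use it to exclude patients from the primary comparison.

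The cost is a few minutes at each existing visit, one case report form item and some instruction wording. Feedback must be neutral so that a correction does not hint at which sites are real. Checks at V2 and V4 are snapshots and do not measure the home rate, but they give a first estimate of m where there is now none. I would not ask for photographs from home: the documents provide neither for their transfer nor for staff to review them.
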